5.7.5. Additional Multivariable Analyses

All pneumonia events will be combined as a secondary pneumonia outcome. Multivariable modeling will be employed on this outcome (all pneumonia) in the same manner as applied to the primary severe pneumonia outcome.

To examine a potential dose-response relationship with ICS-containing medications, the strength of the prescribed ICS medication on the Cohort Entry Date will be categorized into equipotent doses of low, medium, and high-dose ICS based on classification according to Figure 3-1 presented in the Global Initiative for Asthma (GINA) guidelines [GINA, 2011]. The strength of the new user prescription would be entered into the Cox model primary outcome models as low, medium, and high relative to LABD (e.g. dummy variables). Cumulative dose may be considered.

To identify more persistent users, the primary endpoint (severe pneumonia) will be evaluated restricting to patients who are prescribed treatment for greater than 6 months (allowing for 90-day gaps between treatments). Each inhaler can last up to 90 days.

As there may be differential drop out over time, ICS-Containing vs. LABD new users who continue taking medications for at least 6 months may not be clinically similar. Therefore, additional confounders will be identified in the 6-mo period to account for any events that would affect censoring or outcomes (e.g., COPD exacerbations, emergency and non-emergency hospitalization, primary care visits). The PS will be regenerated among the more persistent group to include updated confounders measured in the 6-mo period of persistent use as the new analysis "start". Patients who have an unresolved episode of pneumonia after 6 months of persistent use would be excluded from the persistent analysis. Patients would be required to have at least 14 days between their last pneumonia episode and the persistent analysis "start" date.

All analyses will be performed using SAS [Cary, NC].

If there is sufficient sample size, MRC dyspnea score will be included as a confounder in the primary model (collected 2009 onwards) as part of secondary analyses. Otherwise, it will not be included.

To examine potential differences in patient groups, demographic characteristics of patients with HES linkage vs. those without HES linkage will be compared. It is not expected that there will be clinically significant differences between these groups.

The number of deaths in each treatment group will be described. If available, the cause of death will be summarized for each treatment group.

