5.7.4. Multivariable Modeling

Multivariable analysis will be performed using Cox proportional hazard model with adjustment for confounders and exposures in Section 5.6 and Section 5.7.

The following outcomes will be examined:

- Severe pneumonia events (HAP and Severe CAP combined)
- All pneumonia events

Severe pneumonia events will be examined as the primary outcome. As a secondary outcome, all pneumonia events will be analyzed. The number of confounders can be supported in the modeling will be based on the total number of severe pneumonia and all pneumonia events and their distribution by treatment.

To adjust for differences confounding by severity due to differences in prescribing between ICS-containing medications and LABD, propensity scores (PS) will be utilized. The propensity score will be estimated to model the probability that a chance of a patient receiving ICS-containing medications compared with receiving LABD given a patient's observed set of baseline covariates. The logistic models used to calculate the propensity scores, all available variables in Section 5.5 (exposures) and in Section 5.6 (confounders) will be entered into the model. Propensity scores will be produced.

The PS in both groups would be evaluated for overlap, and patients with scores in the tails of the distribution that were not represented in both groups would be eliminated from the analysis. Patients with extreme PS weights (values >10) will be examined and may be removed from the analysis as their contribution would be influential and affect the model. Patients eliminated from the analysis would be described.

Multivariable analysis will be performed using Cox proportional hazard model with adjustment for the propensity score using inverse probability of treatment weighting (IPTW). This approach is more appropriate then propensity score matching when there may be effect measure modification [Stürmer, 2006]. Because of the cohort design, it is possible to adjust for confounders in the PS approach as well as include them as main effects in the model; however, it has been demonstrated that the addition of confounders with propensity scores does not contribute appreciably to the model [Rubin, 2000; Stürmer, 2006]

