	CerebroVascular Disease			
	Dementia			
	GERD			
	Peptic Ulcer			
	Peripheral Vascular Disease			
	Mild Liver Disease			
	Moderate Liver Disease			
	Connective Tissue Disorder			
	Hemiplegia/Paraplegia			
	Diabetes			

		Hazard Rat	es	
Stratum	Value	Adjusted HR	Lower 95% Cl	Upper 95% Cl
	Diabetes (with complications)			
	Anxiety			
	Depression			
	Cancer (non-metastatic solid tumours, leukemias/lymphomas)			
	Cancer (metastatic solid tumours)			
	Lung cancer			
	Renal diseases			
COPD therapy, severity / frailty	past 12 mos associated with (%)			
	Frequent Oral Corticosteroids			
	Home Oxygen therapy			
	Nebulized therapy			
Other COPD th	erapy in prior 12 (%)			
	SABD			
	Theophylline			
Other Medications	ACE-inhibitors			
	Statins			
	Immunosuppresants			
	Cancer treatment			
All GP visits wi	thin past 12 mo			
	0			
	1-5			

		Hazard Rates				
Stratum	Value	Adjusted HR	Lower 95% Cl	Upper 95% Cl		
	6-10					
	11-15, 16-20, >20					
All Emerger	ncy Hospitalizations, past 12 mo					
	0					
	1-2					
	3+					
All Non-Em mo	ergency Hospitalizations, past 12					
	0					
	1-2					
	3+					
COPD exace	erbations, past 12 mo					
	COPD hospitalisations					
	0					
	1					
	2+					
	Moderate exacerbations					
	0					
	1					
	2+					

1. *Adjustments to these confounders, including re-parameterization of the confounders, may be performed during the analyses as outlined in the analysis plan.

2. Note: This table will be repeated on Final Analysis Population examining All pneumonia events, dose (Low, Medium, High), among persistent users (at least 6 months), and by dose among persistent users.

Table 12	Patient characteristics of Patients with COPD who experience
	Severe Pneumonia, Non-Severe Pneumonia, or No Pneumonia
	within first year

Variable		Severe Events	Non- Severe CAP	No Pneumonia	p-value
N					
Gender	Male, %				
Age in years (%)	45 to 64				
	65 to 79				
	80 and older				
Smoking history (%)	Current				
	Non-Smoker				
	Unknown/Missing				
COPD severity (%)	COPD Dx but spirometry conflicts				
	Gold 0				
	Ι				
	II				
	III				
	IV				
	Unknown				
Asthma history (%)	Yes				
Any Pneumonia episode history (%)	Yes				

Variable		Severe Events	Non- Severe CAP	No Pneumonia	p-value
Number of severe pneumonia episodes (within the baseline period) (N, %)	0				
	1 2				
	3 4+				
Number of severe pneumonia episodes (within the baseline period) (N,	0				
%o)	0				
	2				
	3				
	4+				
Deprivation Quintile	1				
	2				
	3				
	4				
	5				

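### The ICS dose analysis rests on a two-group propensity score that does not balance severity across low, medium and high dose; protection against a false gradient then depends on covariates the protocol may cut.

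*Protocol*

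**What the plan says.** Section 5.7.4 defines one propensity score, from a logistic model for the chance of "receiving ICS-containing medications compared with receiving LABD", and uses it as inverse probability of treatment weights in the Cox model. Patients with weights above 10 are examined and may be removed.

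Sections 5.5 and 5.7.5 then say that the strength of the first ICS prescription "would be entered into the Cox model primary outcome models as low, medium, and high relative to LABD". Table 11 is the multivariable Cox model with propensity score adjustment. Its note 2 says that the table is repeated for "dose (Low, Medium, High), among persistent users (at least 6 months), and by dose among persistent users".

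The protocol names one case in which the score is estimated again: "The PS will be regenerated among the more persistent group to include updated confounders". What changes there is the set of confounders, not the two-group contrast. No dose-level score and no balance check by dose is named.

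The protocol also plans covariates in the outcome model. Section 5.7.4 opens with a Cox model adjusted for confounders, and Table 11 lists GOLD stage, prior pneumonia, BMI, smoking, oral corticosteroids, oxygen, hospitalisations and exacerbations. The same section adds that "it has been demonstrated that the addition of confounders with propensity scores does not contribute appreciably to the model" and lets a variable selection strategy reduce the confounders if the events cannot support them.

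**The concern.** Weights from a binary score make the ICS group as a whole resemble LABD. They do not make low, medium and high dose resemble each other, or make any one of them resemble LABD. The protocol's own worry (section 6) is that ICS goes to patients with more severe COPD. If that also holds for strength, high-dose patients stay sicker than low-dose patients after weighting, and a gradient can appear with no effect at any dose.

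The pooled ICS versus LABD contrast would give no warning, because it remains balanced. The results go to regulators to inform risk minimisation (section 3), and a dose gradient is easily taken as support for a drug effect.

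**Working it through.** **The plan's own figures.** None is given for the dose analysis. The power figures in section 5.7.8 concern ICS versus LABD and reproduce with a two-proportion formula (6,600 LABD, 12,000 ICS, rates per person-year treated as proportions, two-sided 0.05):
- Severe pneumonia, 4 versus 7.4 per 1000: 6,600 × 0.004 + 12,000 × 0.0074 = 115.2 events, power 82.8% (stated 115 and 82%).
- All CAP, 11 versus 16.4 per 1000: 6,600 × 0.011 + 12,000 × 0.0164 = 269.4 events, power 85.2% (stated 270 and 85%).

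They say nothing about comparability across doses.

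**What binary weights do to dose.** Inputs from the protocol: ICS share 12,065/18,742 = 64.4% (Table 1), a binary score, and three dose terms against LABD. Assumed inputs: one standard normal severity score X; log-odds b per SD for ICS versus LABD; log-odds d per SD for higher dose; log-hazard g per SD for pneumonia; ICS users split into thirds by dose; true hazard ratio 1.0 throughout. Each ICS patient is weighted by 1/P(ICS|X) and each LABD patient by 1/(1 − P(ICS|X)). The outcome model has dose terms only. Simulation with 2,000,000 patients:

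| b, d, g | Low | Medium | High | High/low |
|---|---|---|---|---|
| 0.3, 0.3, 0.5 | 0.90 | 1.00 | 1.10 | 1.22 |
| 0.5, 0.5, 0.5 | 0.85 | 1.00 | 1.17 | 1.38 |
| 0.5, 0.5, 0.8 | 0.77 | 0.98 | 1.27 | 1.65 |

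The pooled ICS versus LABD ratio is 1.00 in every row. A hand check on the second row: weighted mean severity is about −0.31, 0.02 and 0.32 SD for low, medium and high, against about 0 in LABD. So exp(0.5 × −0.31) = 0.86 and exp(0.5 × 0.32) = 1.17. With d = 0 there is no gradient.

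**Dose-level weights.** Weighting each patient by 1/P(dose level received|X) returns 1.00 at every dose. At b = d = 0.5 the effective sample size in the high-dose group is about 76% of nominal.

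**Keeping severity in the outcome model.** With binary weights plus severity in five categories, the second row becomes about 0.98/1.00/1.02. In the third row the high-to-low ratio falls from 1.65 to about 1.07. With severity entered as a correctly specified continuous term, the gradient disappears.

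**Can the events carry those covariates?** Table 11, counting asthma once and GP visits as six levels, needs about 61 covariate parameters: 20 for demographics, smoking, asthma, prior pneumonia, GOLD stage, vaccination and BMI; 19 for comorbidities; 9 for medications; 13 for visits, hospitalisations and exacerbations. Adding 3 dose terms gives 64. Severe events are 106 + 1 = 107 (Table 4), so 107/64 ≈ 1.7 events per parameter. For all pneumonia, 283/64 ≈ 4.4.

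**The weight limit of 10.** Unstabilised weights average 1 over the group's share. For ICS as a whole that is 1/0.644 = 1.55. For a third of ICS users it is 3/0.644 = 4.66. A limit of 10 is then about 6.4 times the average in the first case but only 2.1 times in the second.

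**The case against.** A reader might infer that nothing in the plan adjusts for severity between dose levels. The protocol does not support that. Table 11 carries severity covariates as main effects and is the table repeated for dose, and estimating risk-factor effects is itself an objective. If those covariates are kept and reasonably coded, most or all of the gradient goes. The hazard ratios from weights alone are therefore an upper case.

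That protection is not secure. The statement that added confounders contribute little is reasonable for covariates the score has already balanced, but across dose it has not balanced them. Reduction is allowed, and 1.7 events per parameter makes it likely for severe pneumonia. Nothing says severity would be dropped, but nothing protects it either.

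Two further objections stand in part. No sentence states outright that the binary weights are applied to the dose model. That is the plain reading of sections 5.7.4 and 5.7.5 and Table 11, and the analysis plan, to which detail on score generation is deferred, could define a dose-level score. And the protocol has no data linking strength to severity, so the size of any bias is assumed.

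It is also tempting to extend the point to the main result or to the study's conclusions. Neither follows. The pooled estimate is unaffected, dose-response is not one of the four objectives in section 4, and the protocol does not say that a gradient will be read as causal.

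**Conclusion.** The point holds for a secondary analysis. The protocol fixes a two-group score and puts three dose terms into the models that use it, so the weights do not balance severity by dose. What remains is covariate adjustment that the protocol discounts, permits to be cut, and has too few severe events to support in full.

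With no true effect, the false gradient could run from about 0.90/1.00/1.10 to 0.77/0.98/1.27 if weights alone are relied on. It is much smaller if severity covariates stay in. All of this assumes that strength follows severity; without that link there is no gradient. This should be changed before the dose results are produced, but it does not threaten the primary comparison.

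**What to change.** For the dose analyses, in the full cohort and in persistent users:
- Estimate a four-level multinomial propensity score (LABD, low, medium, high) on the same covariates, and use stabilised weights for the level received.
- Restate the limit of 10 for these weights.
- Report covariate balance across all four groups.
- Name the key severity covariates that stay in the dose outcome model whatever other reduction is made.

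Keep the binary score for ICS versus LABD. If dose-level weighting is not adopted, label the dose results exploratory and not balanced across doses.

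The cost is one more model and somewhat wider dose-level intervals. At the 0.5, 0.5 setting, 76% effective sample size in the high-dose group means standard errors for that group larger by about 1/√0.76 = 1.15.

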5.7.6. Comparisons of Patient Characteristics by Pneumonia Status

To evaluate the third objective comparing patients developing severe pneumonia vs. nonsevere pneumonia, a Pneumonia Population will be identified. The first pneumonia (or no pneumonia) within one year following the Cohort Entry Date will be included regardless of censoring in the proportional hazards model. Patients who do not experience pneumonia within the first year will be included in this analysis and counted as having no pneumonia.

As it is also of interest to compare patients who get pneumonia versus those who do not get pneumonia during this period, descriptive summaries will include all three categories: severe pneumonia (severe CAP and HAP combined), non-severe pneumonia, and no pneumonia. To assess differences between pneumonia groups, clinical and patient characteristics will be compared using the chi-square test or chi-square test using the row mean scores differ option in SAS to account for ordered response categories. For continuous measures, nonparametric tests including Wilcoxon rank sum test will be used as they do not require assumptions about normality or equal variance.

Characteristics of patients experiencing pneumonia within the year following Cohort may be compared to those individuals that did not develop and episode of pneumonia using multiple logistic regression modeling in an exploratory fashion in the new user cohort, irrespective of treatment and censoring. Based on the number of events, the number of confounders included in the model will be reduced using a variable reduction strategy to be described in the analysis plan. Treatment will not be included in the logistic regression modeling, as the model will focus on patient characteristics and does not account for treatment discontinuation.

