4. OBJECTIVES

The overall objectives of this retrospective observational COPD cohort study are:

- to estimate the magnitude of association between risk factors and pneumonia requiring hospitalization, including ICS-containing medications
- to evaluate if ICS-containing medications modify the effect of risk factors for severe pneumonia (i.e. evaluate statistical interaction between ICS × other risk factors)
- among patients with pneumonia, to evaluate any differences in clinical characteristics between patients who have severe pneumonia (requiring hospitalization or contracted in hospital) relative to those with non-severe community acquired pneumonia that did not require hospitalization in the one-year prior following new user Cohort Entry
- to evaluate any differences in clinical characteristics between patients who develop pneumonia or severe pneumonia vs. those who do not develop pneumonia in the one year period following new user Cohort Entry

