a. Treatment groups will be compared on baseline characteristics using chi-square test row mean scores differ for categorical variables to take advantage of the ordering for ordinal categories.

Table 13Patient Co-morbidities and Medications used in the period prior to
Severe vs. Non-Severe Pneumonia Diagnosis – Pneumonia
Population

Variable	Severe Events	Non-Severe CAP	No Pneumonia	p-value
N				
Vaccination (%)				
Influenza in the past 12 mo				
Pneumococcal in the past 5 years				
BMI mean (SD)				
Underweight (<18.5),				
Low Normal (18.5-≤20.9)				
High Normal (21 - ≤24.9)				
Overweight (25.0 - ≤29.9)				
Obese (>30.0)				
Comorbid conditions (%)				
Asthma				
Myocardial Infarction				
Congestive Heart Failure				
CerebroVascular Disease				
Dementia				
Peptic Ulcer				
Peripheral Vascular Disease				
Mild Liver Disease				
Moderate Liver Disease				
Connective Tissue Disorder				

Variable	Severe Events	Non-Severe CAP	No Pneumonia	p-value
Hemiplegia/Paraplegia				
Diabetes				
Diabetes (with complications)				
Anxiety				
Depression				
Cancer (non-metastatic solid tumours, leukemias/lymphomas)				
Cancer (metastatic solid tumours)				
Lung cancer				
Renal diseases				
COPD therapy in prior 12 months associated with severity (%)				
Oral Corticosteroids				
Home Oxygen therapy				
Nebulised therapy forms				
Other medicines in prior 12 months (%)				
ACE-inhibitors				
Statins				
Immunosuppresants				
Cancer treatment				

Variable	Severe Events	Non-Severe CAP	No Pneumonia	p-value
All GP visits within past 12 mo				
0				
1-5				
6-10				
11+				
All Emergency Hospitalizations within past 12 mo				
0				
1-2				
3+				
All Non-Emergency Hospitalizations within past 12 mo				
0				
1-2				
3+				
COPD exacerbations within prior 12 mo				
COPD hospitalisations				
0				
1				
2+				

Variable	Severe Events	Non-Severe CAP	No Pneumonia	p-value
Moderate exacerbations				
0				
1				
2+				

1. *Tables will be updated to match protocol any adjustments to the analysis based on the analysis plan.

Table 14Exploratory Analysis: Factors Associated with Severe Pneumonia
vs. No Pneumonia during multivariable logistic regression-within the
first year

		Odds Ratio			
Stratum	Value	Adjusted OR	Lower 95% CI	Upper 95% CI	
Overall					
Gender	Female (reference)				
Age	45 to 64				
	65 to 79				
	>= 80				
Smoking	Current				
	Past				
	Never / Non-smoker (reference)				
	Unknown				
Asthma history	Yes				
Prior	Yes				
pneumonia					

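### No test or estimate is tied to severe versus non-severe pneumonia (objective 3): Tables 12 and 13 give one p-value for three groups, and as a three-group test it mostly weighs pneumonia against none

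*Protocol*

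**What the plan says.** Section 4 states the third objective as "among patients with pneumonia, to evaluate any differences in clinical characteristics between patients who have severe pneumonia" and those with non-severe community-acquired pneumonia. The fourth objective is a different question: patients who develop pneumonia, or severe pneumonia, against those who do not.

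Section 5.7.6 starts from the third objective: "To evaluate the third objective comparing patients developing severe pneumonia vs. nonsevere pneumonia, a Pneumonia Population will be identified". It then brings the pneumonia-free patients into the same analysis, so that "descriptive summaries will include all three categories: severe pneumonia (severe CAP and HAP combined), non-severe pneumonia, and no pneumonia". The testing sentence reads "To assess differences between pneumonia groups, clinical and patient characteristics will be compared using the chi-square test", or the row-mean-scores version for ordered categories. It adds "For continuous measures, nonparametric tests including Wilcoxon rank sum test will be used". Neither sentence names the groups being contrasted.

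In Section 8, Table 12's title covers "Severe Pneumonia, Non-Severe Pneumonia, or No Pneumonia", and Table 13's column heads are "Severe Events Non-Severe CAP No Pneumonia p-value". Each table has three group columns and one p-value column. Table 13's title nevertheless refers to "Severe vs. Non-Severe Pneumonia Diagnosis" in the Pneumonia Population and to the period before that diagnosis. The only regression, Table 14, sets severe pneumonia against no pneumonia and may be repeated for all pneumonia against none.

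**The concern.** Objectives 3 and 4 are separate questions, and one p-value per row cannot answer both. The no-pneumonia column holds roughly 18,000 patients and the two pneumonia columns a few hundred at most, so a test across all three responds mainly to whether pneumonia patients differ from everyone else. The Introduction already lists older age, low BMI, current smoking and comorbidity as known risk factors for pneumonia. Small p-values in those rows are therefore to be expected, whatever their relation to severity.

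At stake is the reading of the table meant to show which pneumonia patients end up in hospital. The Rationale promises that result and says the findings may inform risk minimisation; Section 3 says they go to regulators. A row could be taken as a marker of severity when it is only a marker of pneumonia. A real severe versus non-severe difference could also be diluted.

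Table 13 has a labelling fault as well. Section 5.7.3 defines the Pneumonia Population as patients with at least one event, so a table of that population cannot contain a no-pneumonia column. Nor do pneumonia-free patients have a diagnosis date before which covariates could be measured.

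**Working it through.** **The protocol's own figures.** The only power figures (Section 5.7.8) are for ICS against LABD. Both reproduce with a two-proportion formula at 6,600 and 12,000 patients:
- 11 versus 16.4 per 1,000 gives 85.2% power and 269.4 events (stated: 85%, 270).
- 4 versus 7.4 per 1,000 gives 82.8% power and 115.2 events (stated: 82%, 115).

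No figure is given for severe versus non-severe.

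**Inputs.**
- Table 4: 106 severe CAP + 1 HAP = 107 severe; 176 non-severe; 107 + 176 = 283.
- Table 1: 18,742 new users, so 18,742 − 283 = 18,459 without pneumonia.
- These are first events before censoring over all follow-up. The Pneumonia Population counts first events within one year regardless of censoring, and its size is not stated, so the counts are a proxy.
- The protocol gives no prevalences by group; all those below are assumptions.

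**Splitting the three-group chi-square (2 df).** Let p̄ be the overall prevalence, d the severe minus non-severe difference, and D the pneumonia minus none difference. The noncentrality is [w1·d² + w2·D²] / [p̄(1 − p̄)], with
- w1 = 107 × 176 / 283 = 66.5 (severe versus non-severe)
- w2 = 283 × 18,459 / 18,742 = 278.7 (pneumonia versus none)

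The ratio is 278.7 / 66.5 = 4.2. For differences of equal size, 278.7 / (66.5 + 278.7) = 81% of the weight lies on pneumonia versus none.

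**Chance of p < 0.05 when severe and non-severe are identical (d = 0).** For 25% / 25% / 15%: p̄ = (283 × 0.25 + 18,459 × 0.15) / 18,742 = 0.1515, p̄(1 − p̄) = 0.1286, and the noncentrality is 278.7 × 0.10² / 0.1286 = 21.7. Other noncentral chi-square results:

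| Severe / non-severe / none | 107/176/18,459 | 60/100/18,500 (assumed) |
|---|---|---|
| 25% / 25% / 15% | 0.99 (noncentrality 21.7) | 0.89 |
| 20% / 20% / 12% | 0.96 (noncentrality 16.7) | 0.80 |

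Simulation with 20,000 tables per scenario:

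| Severe / non-severe / none | 107/176/18,459 | Half the events, 53/88/18,601 |
|---|---|---|
| 20% / 20% / 10% | 0.995 | 0.91 |
| 30% / 30% / 20% | 0.95 | 0.74 |
| 35% / 35% / 25% | 0.93 | 0.68 |

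In the simulated scenarios a direct severe versus non-severe test rejects about 5% of the time, as it should.

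**Dilution of a real difference.** For 30% severe against 20% non-severe, with the no-pneumonia group at the cases' average (23.8%), the three-group test has 38% power and the direct test 48%.

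**Power of the direct contrast.** At 107 versus 176: about 48% for 30% versus 20%, and about 80% for 35% versus 20%. At 53 versus 88: about 28% and 51%.

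**The case against.** The strongest reply is that the protocol nowhere calls the p-value a three-group test. Section 5.7.6 opens with severe versus non-severe, its wording on differences between groups allows pairwise tests, the Wilcoxon rank sum test compares two samples, and Table 13's title names two groups. This stands: the three-group test is the natural reading of the layout, not a stated rule. It does not remove the problem, because none of these hints assigns the p-value to objective 3.

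Second, the two pneumonia columns sit side by side. A reader who sees 25% and 25% against 15% can tell that the factor does not separate severe from non-severe. One might infer that objective 3 goes unanswered or is bound to be answered wrongly. The documents do not support that, since it is still addressed descriptively. Nor does a small p-value carry no information on severity; that component keeps about 19% of the weight.

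Third, the missing severe versus non-severe regression is no oversight. The revision chronology gives the small number of events as the reason. That explains the lack of a model, but not of a simple two-group comparison.

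Fourth, Section 5.7.9 and Table 13's footnote allow refinement in the analysis plan. That is fair for detail, but the protocol itself fixes a display that does not match its objective.

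Finally, Table 13's title could suggest that visits and exacerbations will be counted up to diagnosis in cases and up to cohort entry in non-cases. Section 5.6 ties those counts to the year before Cohort Entry, so this is a labelling error, not planned differential measurement.

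**Conclusion.** The point holds as a mismatch between objective and display: no test or estimate is assigned to severe versus non-severe, and the groups behind the single p-value are undefined. The numerical consequence is conditional on a three-group test. In that case about 81% of the weight, for equal-sized differences, lies on pneumonia versus none. This share hardly moves if both event counts are halved. A factor unrelated to severity would often be flagged: about 0.8 to 0.99 under the 25/25/15 and 20/20/12 prevalences, and 0.68 to above 0.99 across all scenarios, the lowest with half the events. These probabilities rest on assumed prevalences and on Table 4 standing in for the one-year counts, so they show the direction and rough size of the problem and do not predict the study's results. The analysis is descriptive and secondary to the Cox models, which are unaffected. It is still worth correcting before the tables are produced.

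**What to change.** In Section 5.7.6 and the shells of Tables 12 and 13, replace the single p-value with two labelled contrasts:

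- (a) Severe versus non-severe within the Pneumonia Population, as an unadjusted difference or odds ratio with 95% CI, for objective 3. Given the few events, no multivariable model is needed.
- (b) Pneumonia, and severe pneumonia, each versus no pneumonia, for objective 4.

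Retitle Table 13 so that all three columns use covariates anchored to the Cohort Entry Date, as in Section 5.6, and label its population as the New User Cohort Free of Pneumonia at Index Date.

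The cost is a few sentences and one or two extra columns from data already held. The drawback is that contrast (a) will be imprecise, with about 48% power for 30% versus 20% at 107 and 176 patients and less if the one-year counts are smaller. An interval shows that openly, and a non-significant result should not be read as evidence of no difference.
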